3.1 Duration of clinical study

The study will involve three on-site visits over a period of up to eleven weeks.

3.2 Duration of clinical study per Participant

- Screening: 1 - 7 days
- Run-in phase: 14 days
- Intervention phase: 56 days
- Total time: 77 days

4 Participants and site

4.1 Number of Participants

Screen n = 160

Randomize n = 80 (Two arms with 40 subjects per group)

Evaluable n = 72

Expected dropout rate is 10% - dropouts will not be replaced.

4.2 Clinical study population

Otherwise, generally healthy adults aged 18 to 65 who regularly experience constipation.

4.3 Inclusion criteria

To be eligible for inclusion, the Participant must fulfil all the following criteria:

1. Is willing to participate in the study and comply with its procedures.
2. Be able to give written informed consent.
3. Adults aged ≥ 18 years and ≤ 65 years.
4. Experience less than 3 bowel movements per week within the past three months.
5. $\geq 25\%$ of bowel movements with stool firmness, less than Type-3 based on Bristol Stool Scale (BSS), within the past three months.
6. Record less than 6 bowel movements in eDiary App during the two-week run-in period.
7. Is willing to maintain the current diet and level of physical activity throughout the study period.

4.4 Exclusion criteria

Participants will be excluded from the study if they meet any of the following criteria:

1. Participants who are pregnant or wish to become pregnant during the study, or who are currently breastfeeding.

2. Participants currently of childbearing potential, but not using continuous effective method of contraception, as outlined below:
 - a. Complete abstinence from intercourse two weeks prior to administration of the Study Product, throughout the clinical study, until the completion of follow-up procedures or for two weeks following discontinuation of the Study Product in cases where Participant discontinues the study prematurely. (Participants utilizing this method must agree to use an alternate method of contraception if they should become sexually active and will be queried on whether they have been abstinent in the preceding two weeks when they present to the clinic for the final Visit).
 - b. Has a male sexual partner who is surgically sterilized prior to the Screening Visit and is the only male sexual partner for that Participant.
 - c. Sexual partner(s) is/are exclusively female.
 - d. Use of acceptable method of contraception, such as a spermicide, mechanical barrier (e.g., male condom, female diaphragm), tubal ligation, or contraceptive pill. The Participant must be using this method for at least one week prior to and one week following the end of the study.
 - e. Use of any intrauterine device (IUD) or contraceptive implant. The Participant must have the device inserted at least two weeks prior to the first Screening Visit, throughout the study, and two weeks following the end of the study.
3. Participants reporting current, or historical alcohol or drug abuse in past year.
4. Participants who have quit smoking in the 6-months prior to screening.
5. Participants with a known allergy to the Study Product's active or inactive ingredients.
6. Participants with a chronic disease who require long-term medication throughout the whole study period.
7. Participants with a significant acute, chronic or un-controlled coexisting illness or is taking medication/supplements that would put the Participant at risk or confound the interpretation of the study results, as judged by the investigator.
8. Participants who regularly take medications, that are thought to affect defecation, including regular laxative use. (Occasional laxative use (PRN) < 3 times per month is acceptable).
9. Participants who regularly consume supplements that are thought affect defecation, including but not limited to fiber, iron, and magnesium.
10. Participants who are consuming oral antibiotics at screening, during run-in and for the duration of the study.
11. Participants who have consumed probiotic supplements and prebiotic supplements eight weeks prior to Visit 2.
12. Participants who have consumed fermented foods, that aid in bowel movement improvement such as yogurt, kefir, sauerkraut, kimchi, soy-based fermented food, miso, natto and fermented cheese, etc. within the four weeks prior to the Visit 2.
13. Participants who are diagnosed with or undergoing treatment for any gastrointestinal conditions such as coeliac disease, diarrhea, Crohn's disease, ulcerative colitis, irritable bowel syndrome, diverticulosis, stomach or duodenal ulcers, gastroesophageal reflux disease (GERD) or have undergone significant gastrointestinal surgery (appendectomy allowed).

14. Participants diagnosed with clinical depression, Parkinson's disease, anxiety or an anxiety related disorder, who are undergoing treatment with medication.
15. Participants with clinically significant abnormal laboratory results at screening.
16. Individuals who are cognitively impaired and/or who are unable to give informed consent.
17. Participants may not be participating in other clinical studies. If the participant has previously taken part in an experimental study, the Investigator must ensure sufficient time has elapsed before entry to this study to ensure the integrity of the results.
18. Any Participant who is an employee of the investigational site or an Atlantia Clinical Trials employee or their close family member or a member of their household.
19. Individuals who, in the opinion of the investigator, are considered to be poor attendees or unlikely for any reason to be able to comply with the study.

4.5 Randomization, blinding, and treatment allocation

Participants who meet the eligibility criteria/have successfully completed the Screening Visit will be randomized on a 1:1 basis to the two arms of this study to determine whether they receive the Study Product (SP) or the Placebo. The randomization list and procedure will be prepared by a statistician not involved in the conduct phase of the study (i.e., blinded data reviews) and securely conveyed to the science and quality team.

Randomization will be completed using a minimization procedure via an Interactive Web Response System (IWRS) with the aim to minimize imbalance on sex and bowel movement frequency. Each eligible participant will be assigned a randomization number, which corresponds to one of the two products. The relationship between the randomization number and the product assignment will be unknown to the clinical research team, the sponsor, study site staff, or the Participants, i.e., the study will be double blinded.

Blinding of both study team and Participants will be ensured by only providing access to the randomization list to the science and quality team which is stored in the quality drive.

4.6 Emergency Unblinding procedure

The investigator will receive access to an IWRS to unblind if required.

Unblinding access is for emergency use only, i.e., when it becomes absolutely necessary to know what treatment the participant receives in case of a serious adverse event (SAE) in order to manage the participant's condition. A broken code requires the participant to be withdrawn from the clinical trial.

The investigator should promptly document and notify the Sponsor any premature unblinding (e.g., accidental unblinding, unblinding due to a SAE) of the IP. The date, time, and reason for unblinding must be written onto the envelope and signed by the investigator.

If appropriate, the monitor will check the IWRS during monitoring visits and obtain adequate documentation for any unblinding.

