2.1.1 Primary endpoint

Change in mean weekly frequency of SBM, as measured by the daily bowel diary from baseline to the end of intervention. Frequency will be defined as the mean weekly number of SBM during the 2-week run-in period prior to Visit 2, for baseline, and during the final 2-week period of the intervention prior to Visit 3, for end of intervention.

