5.9 Rescue Medication

In case of no bowel movement for more than four days: bisacodyl suppositories or tablets (5- 10 mg) or other rescue medication in line with local guidelines at the dose specified in the local guidelines (no more than three consecutive days over a period of 1 week) will be allowed as rescue medication. Maximum dosage: 15 mg/ day.

Its use needs to be documented at relevant study visits (including concomitant medication, diet, supplements, and any related adverse event). The date and time of rescue medication administration as well as the name and dosage regimen of the rescue medication must be recorded.

The study site will not supply any rescue medication.

6 Study Procedures

Table 2. Schedule of Assessments

Assessment periods						
Visit Number	Visit 1	Run-in	Visit 2	Visit 3	Early Termination Visit	
Visit Window	Day -21 to -15	Day -14 to -1	Day 0	Day 56 + 3 Days		
Study Phase	Screening	Run-in	Intervention			
Screening						
Informed consent	x					
Eligibility Screen	x		x			
Demographic/ Lifestyle data	x					
Medical history	x		x		x	
Anthropometric measurements (Height, weight, BMI)	x					
Prior and concomitant medications	x		x	x	x	
Safety and Tolerability						
Vitals (Blood pressure, heart rate, temperature)	x		x	x	x	
Safety blood parameters	x					

Assessment periods						
Visit Number	Visit 1	Run-in	Visit 2	Visit 3	Early Termination Visit	
Visit Window	Day -21 to -15	Day -14 to -1	Day 0	Day 56 + 3 Days		
Study Phase	Screening	Run-in	Intervention			
(Chemistry profile and Hematology profile)						
AE/SAE			<----->		x	
Assessments/Procedures						
Stool sample collection						
Dispense stool collection kit	x		x			
Return Stool Sample for microbiome analysis			x	x	x	
Urine collection						
Urine pregnancy test	x		x	x	x	
Questionnaires						
Download eDiary App	x					
Bowel Movement & Bristol Stool Scale		x	<----->			
PAC-SYM (Week 0, 4 & 8)			<----->			
PAQ-QoL (Week 0, 4 & 8)			<----->			
Delete eDiary App				x	x	
Dietary analysis						
Dispense 3-Day food Diary	x		x			
Return 3-Day food Diary			x	x	x	
Supplementation						
Randomization			x			
Administer SP			x			
Return SP				x	x	
Assess SP Compliance				x	x	
Participant Compensation						
Dispense Participant Compensation				x	x	

All visits will have the option of being completed remotely via telephone where feasible based on the assessments required for the visit.

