7.1 Daily eDiary Questions

Participants will download an eDiary App at Visit 1 which they will be directed to complete throughout the study. This eDiary will record the following information:

- Bowel movement diary will collect daily data relating to stool frequency and stool consistency.
- AEs and medication use (Weekly)
- Study Product compliance (Weekly)

7.2 eDiary Questionnaires

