8.4 Analysis of Samples

All samples will be analyzed using validated assays and methods.

9 Early Participant Withdrawal

Participants have the right to withdraw from the study at any time for any reason, without giving a reason and without penalty or loss of benefits they are entitled to. The PI/Sub-Investigator also has the right to discontinue Participants from SP consumption and/or withdrawal from the study if this is in the best interest of the Participant or if Participant is persistently not compliant with study procedures and SP consumption.

Any of the following conditions may lead to premature withdrawal from SP/study:

- Request by Participant to discontinue for any reason during the study.
- erroneously included / randomized Participant.
- adverse event(s) or concurrent illness that, in the opinion of the PI/Sub-Investigator, warrants the Participant's withdrawal from intervention.
- intake of concomitant medication/dietary supplements prohibited by the protocol.
- Participants who do not follow the requirements of the Protocol, especially those concerning safety and/or if the Participant after their enrolment is uncooperative or not willing to comply with the protocol (non-compliant).

- failure to return for follow-up visits despite numerous attempts to reschedule (lost to follow-up).
- request by regulatory agencies for termination of supplementation of an individual Participant or all Participants under this protocol.
- pregnancy, if a protocol exclusion criterion.

The circumstances of any discontinuation will be in consultation with the Sponsor and must be documented in detail in the corresponding study termination form in the case report form. Whenever a Participant will be withdrawn from the study for whatever reason, adequate efforts will be made to perform a final assessment to include standard medical and laboratory tests which would have been done on normal completion of the study. The data of the withdrawn Participants will be documented in the clinical study report.

Note: Participants who withdraw prematurely from the study will not be replaced.

10 Data processing

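### Removal from the study before about Day 43 leaves no observed primary outcome, because the diary stops when participation stops

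*Protocol*

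**What the plan says.** Four parts of the protocol bear on this.

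- **Endpoint (Section 2.1.1).** The end-of-intervention value is the mean weekly number of SBMs from the daily diary "during the final 2-week period of the intervention prior to Visit 3". Section 5.5.1 places Visit 3 on Day 56, and Table 2 allows up to three days later.
- **Diary (Section 7.1 and Table 2 in Section 6).** "Participants will download an eDiary App at Visit 1 which they will be directed to complete throughout the study". Table 2 has a row "Delete eDiary App", marked at Visit 3 and at the Early Termination Visit.
- **Code break (Section 4.6).** "A broken code requires the participant to be withdrawn from the clinical trial". The sentence has no exception and concerns the trial as a whole, not only product.
- **Withdrawal (Section 9).** The investigator may "discontinue Participants from SP consumption and/or withdrawal from the study" in the participant's best interest or "if Participant is persistently not compliant with study procedures and SP consumption". A separate list opens with "Any of the following conditions may lead to premature withdrawal from SP/study". Neither part says when product alone is stopped and when study participation ends. The exit assessment it asks for consists of medical and laboratory tests.

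**The concern.** The primary outcome lies entirely at the end of the 56 days and exists only as daily app entries. Under the wording above, some participants leave the study through a decision of the protocol or the site, not by their own choice, and the collection tool is then removed. An assessment made on the day of leaving cannot supply stool counts for days still to come.

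Earlier diary periods (Weeks 1-2, 3-4 and 5-6, Section 2.2.1) are kept and could inform a model. But no analysis plan can recover primary-window days that were never recorded, so this has to be settled in the protocol. The entry is made at home and needs no visit, so this part of the loss is avoidable. Loss through participant request or loss to follow-up is a different matter, and no wording would recover it.

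**Working it through.** **Planned numbers.** Section 4.1 gives 80 randomized, 10% dropout and 72 evaluable. 80 × 0.10 = 8 and 80 − 8 = 72; equally 72 / 0.90 = 80. The plan's own figure reproduces.

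**Primary window.** With Visit 3 on Day 56:
- visit day included: 56 − 13 = 43, so Days 43-56;
- visit day excluded: 56 − 14 = 42, so Days 42-55.

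With Visit 3 on Day 59, the latest day allowed, the window starts on Day 46 or Day 45 respectively.

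**Days observed by last diary day (Visit 3 due on Day 56).**

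| Last diary day | Days in 43-56 | Days in 42-55 |
|---|---|---|
| 41 or earlier | 0 | 0 |
| 42 | 0 | 1 |
| 43 | 1 | 2 |
| 49 | 7 | 8 |
| 55 | 13 | 14 |

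So about Day 43 is the right boundary on either count.

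**Who falls on the wrong side of it.**
- *Code break:* study withdrawal is mandatory (Section 4.6), so the diary ends.
- *Investigator decision:* the diary ends if the choice is study withdrawal. If the choice is product only, the participant is still in the study and Section 7.1 still directs diary completion.
- *Participant request or loss to follow-up:* no wording would recover these.

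**Illustration of size.** Assumption, not in the documents: the exit day is uniform over Days 1-56, the diary is kept through the exit day, and the window is Days 43-56.
- No window day: 42/56 = 75% (41/56 = 73% if the window is Days 42-55).
- 1 to 13 days: 13/56 = 23%, with mean (1 + … + 13)/13 = 7 days.
- All 14 days: 1/56 = 2%.

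The documents do not say how many exits come from these rules. Call that number m. The expected number with no primary outcome is 0.75 × m:

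| m | Expected with no primary outcome |
|---|---|
| 0 | 0 |
| 2 | 1.5 |
| 4 | 3 |
| 8 | 6 (6/80 = 7.5%) |

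These are expected values, not limits. With m = 8 and every exit before the window, the figure would be 8/80 = 10%, and m itself could exceed the planned 8. Alpha, power, effect size and standard deviation are not given in the protocol, so no effect on power is calculated.

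**The case against.** The best reply is that little in the protocol forces this loss. The one mandatory rule, in Section 4.6, applies to emergency unblinding for a serious adverse event among 80 otherwise healthy adults over eight weeks, so code breaks should be very few. Section 9 is permissive, involves the sponsor and already allows a product-only stop. The sample size also allows for eight losses. All of that stands and limits the size of the point. It does not remove it: after a code break the product-only option is not available, and elsewhere nothing directs the investigator to prefer it.

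That the diary ends at exit is an inference from app deletion and from diary completion being tied to the study. No passage says it outright, but none provides for entries after exit.

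Three stronger readings are tempting and not supported.
- *That the loss is informative or differs by arm.* The adverse-event item in Section 9 speaks of withdrawal from the intervention, and Section 5.5.1 of discontinuing product. Both mainly describe people who can stay in the study and keep the diary. Nothing shows a difference between arms.
- *That Section 9 conflicts with the ITT rule in Section 5.6.* Section 5.6 assigns people to analysis sets, while Section 9 governs conduct. A withdrawn participant can still belong to an as-randomized set.
- *That planned dropout caps the loss at 8.* Section 4.1 gives an expected rate for all causes together, not a maximum.

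On the remedy, it is fair to say that Section 11.3, which lets a pregnant participant leave product but remain in the study, is thin precedent because it provides only for safety monitoring. Self-reported entries after unblinding may also be biased.

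**Conclusion.** The point holds in limited form. Anyone removed from the study after a code break or by the investigator before about Day 43 has no observed primary outcome. Anyone removed later in Weeks 7-8 has a partial one. Participants who only stop product are unaffected.

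The number is unknown and probably small. The only anchor is 8 expected dropouts of 80 from all causes, which the protocol does not divide by reason. The 75% share depends wholly on the assumed uniform exit time. No bias or power consequence is claimed. The case for acting is that the missing days could be observed at little cost and cannot be restored at the analysis stage.

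**What to change.** Leave the rules on when to unblind and when to stop product as they are. Reconcile Sections 4.6, 6 (Table 2), 7.1 and 9 as follows.

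1. State that a code break or an investigator-initiated stop does not by itself end data collection. The sentence in Section 4.6 needs amending for this, because it now ends trial participation as a whole. It states no separate consequence for product; the sponsor would have to word that, and none is proposed here.
2. Ask such participants, if they consent, to continue the bowel diary, PAC-SYM and PAC-QoL to Day 56.
3. In Table 2, delete the App early only when consent to further data collection is withdrawn.
4. For participants with no Visit 3, use Days 43-56 as the end-of-intervention window and keep Section 2.1.1 unchanged for completers. Note that completers' windows may shift by up to three days with the date of Visit 3.
5. Flag entries made after a code break for a sensitivity analysis.

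The cost is protocol and consent wording, and a few participants keeping an app already on their phone for up to eight weeks. Some will decline, and entries after unblinding may carry reporting bias if the participant learns the allocation; item 5 lets that be examined.

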4.7 Number of sites

This is a single-site study, with all Participants to be recruited by Atlantia Clinical Trials.

5 Study Product and Supplementation Regimen

5.1 Study Product

5.1.1 Study Product name and formulation

- Product name: Bifidobacterial capsule, Morinaga Milk Industry, [name].
- Active compound: *Bifidobacterium longum*, 1×10^{10} CFU
- Capsules: 5×10^9 CFU active compound per capsule

5.2 Other product name and formulation

5.2.1 Placebo Product:

- Ingredients: 0 CFU compound per capsule

5.3 Packaging and labelling

The label will contain the following information:

Atlantia Study Code - AFCRO-171

Sponsor: Morinaga Milk Industry

Participant Randomization Code

Investigator name

For clinical study use only

Batch/Lot number

Storage conditions / keep away from children (if applicable)

Directions for use

Emergency Contact Number

Expiry date

Packaging will be performed by Morinaga Milk Industry and labelling will be carried out by Atlantia Clinical Trials, [name].

Each aluminum bag will contain 28 capsules of either the SP or the Placebo. Each Participant will be provided with five aluminum bags (total 140 capsules) allowing for two capsules per day, for 56 days and an extra 14-day supply, in case of delay of visit or loss of Study Product.

5.4 Handling and storage conditions

Study Product will be stored in a secure area with restricted access. The Principal Investigator/Sub-Investigator agrees that the Study Product will be dispensed only to study Participants who have provided written consent. Compliance will be monitored by return of all product containers (used and unused). Any deviations will be noted in the source documents and the Participant's eCRF. The Study Product should be stored at refrigerated temperature, 2°- 8°C (36°-46°F) before being dispensed to the Participants.

Study Participants will be instructed to store the Study Product at room temperature.

5.5 Supplementation regimen

5.5.1 Dosage regimen and dose adjustment

- Participants will be provided an eight-week supply of Study Product (5 bags) at Visit 2 in a transparent UniPak, wherein 4 bags will be used for consumption during the eight-week intervention period and 1 bag will be provided as an additional supply in case of delay in study visit or loss of Study Product.
- Participants will be instructed to consume two capsules of the Study Product per day, before breakfast, with a glass of water for the duration of the study (56 days).
- If the dose is missed, the Participant should consume the same dosage after dinner on the same day.
- Missed doses should not be moved to the following day.
- Participants will be instructed to return any unused Study Product at Visit 3.
- Participants will consume their first dose of Study Product on the day following their Visit 2 (Day 1) and will consume their final dose of Study Product on the morning of their Visit 3 (Day 56).

In the event of significant worsening, severe or intolerable new GI symptoms, or other AEs after product consumption/use or overdose, the dose may be interrupted or titrated after consultation with the sponsor representative and PI/Sub-Investigator. The dose may be temporarily interrupted for the shortest time possible without increasing the risk to the Participants continued safety on the study. If the Participant requires dose interruption for more than three days with no improvement in GI symptoms and/or other AEs, then consultation with the Sponsor representative and PI/Sub-Investigator must occur, and the Participant may be discontinued from SP.

